4.3.3 Intervention fidelity control

Standardised training: all staff complete a unified training programme covering intervention protocol details, safety procedures, and data-recording requirements, culminating in practical and written examinations. An intervention operations manual specifies step-by-step procedures. **Process monitoring:** monthly random audits via on-site observation or video-log review assess protocol adherence. The smart platform automatically logs training data for weekly cross-referencing against the planned schedule. Participants complete brief weekly training diaries. **Fidelity assessment:** a checklist scoring key execution points (warm-up guidance, technique correction, intensity compliance) targets an average score of $\geq 90\%$.

4.4 Primary and Secondary Outcome Measures

4.4.1 Primary outcomes (T2)

BMD: Lumbar spine BMD (g/cm^2) measured by DXA (e.g., GE Lunar Prodigy), reported as absolute values and percentage change from baseline. Within-day coefficient of variation for lumbar spine BMD is approximately 1%.

Physical function: SPPB total score (0–12), comprising standing balance, 4-metre gait speed, and five-times chair-stand subtests (each scored 0–4).

Quality of life: SF-36 Physical Component Summary (PCS) and Mental Component Summary (MCS), each scored 0–100.

4.4.2 Secondary outcomes

Fall incidence (cumulative falls recorded via smart-terminal feedback and monthly follow-up; incidence rate ratio [IRR] with 95% CI). FES-I (16–64; score ≥ 23 indicates fear of falling). Grip strength (HGS, kg; measured at T0, T1, T2; ΔHGS used for mediation analysis). Pain (VAS, 0–10). Intervention process and safety indicators: mean training adherence, mean training dose, and adverse-event frequency and severity.

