3.3.2 Dependent variables

Primary outcomes: (a) BMD (g/cm^2) measured by DXA at the lumbar spine, reported as absolute values and percentage change from baseline; (b) physical function assessed by SPPB total score (0–12), 4-metre gait speed (m/s), and five-times sit-to-stand test (seconds); (c) QoL assessed by SF-36 physical component summary (PCS) and mental component summary (MCS) scores (0–100).

Secondary outcomes: fall incidence (monthly fall diaries and telephone follow-up), Falls Efficacy Scale–International (FES-I, 16–64), grip strength (HGS, kg), and visual analogue scale for pain (VAS, 0–10). Supplementary assessments include TUG, Berg Balance Scale, and the Chinese Osteoporosis Screening Scale (SSS-CN).

Mechanistic indicators: ΔHGS (change in grip strength from baseline to 8 months), analysed as a mediator of BMD improvement.

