4.3 Intervention Protocol and Control Measures

4.3.1 Intervention group (smart community resistance training)

Table 4.3.1 (1), Resistance training program

Program Framework	Implementation Methods	Specific content	
Pre-implementation assessment	The researchers, orthopedic physicians, and nurses jointly evaluated	1. Detailed medical history and physical examination to exclude contraindications to exercise (such as severe cardiovascular disease, history of cerebral infarction, etc.) 2. Muscle function, exercise ability, exercise level, etc. 3. Whether there are diseases that restrict exercise, such as knee osteoarthritis, bone deformity, etc., whether there are mental disorders, intellectual disabilities, etc.	
Resistance Training Program		Exercise intensity	Moderate intensity (12-13 points on the PRE scale)

			
- Starting intensity: 50-60% 1RM (RPE 3-4)
 
- After advancement: 70-80% 1RM (RPE 5-6)
 
- Breathing principle: exhale with force, inhale with relaxation

		Exercise frequency	
3 times/week, 1-2 sets of each exercise, 10-15 repetitions per set;
 
1-4 weeks 1 set of each exercise (10-15 repetitions/set)
 
5-12 weeks 2 sets of each exercise (10-15 repetitions/set)
 
Based on the training manual

		Exercise time	
5 minutes of warm-up, 40 to 60 minutes of resistance training (including interval rest time, 2 to 3 minutes rest between each set), and 5 minutes of stretching and relaxation.

		Sports Tools	
4 types of elastic bands.
 
Yellow is 10 pounds (about 4.5 kg)
 
Pink is 15 pounds (about 6.75 kg)
 
Blue is 20 pounds (about 9.07 kg)
 
Purple is 30 pounds (about 13.6 kg)
 
According to the patient's repetition of 10 to 15 times combined with the PRE dosage to reach a moderate intensity, the elastic band with corresponding load is given.

		Specific actions	
1. Warm-up exercises: including neck stretching, chest expansion exercises, hip rotation exercises, knee twisting exercises, and marching in place, etc.
 
2. Resistance exercises: including waist and back exercises, lower limb exercises, and upper limb exercises. See Table 4.3.1 (2) for specific resistance exercise movements
 
3. Relaxation: stretching, massaging, patting, shaking, and relaxing the limbs with breathing.

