Periodised progression follows dual-indicator control: volume progression (one additional set per exercise every 4 weeks, maximum 3 sets), intensity progression (resistance-band upgrade when RPE ≤ 4 with 15 standard repetitions), and density progression (inter-set rest reduced from 120 seconds to 75 seconds after week 12).

Smart components: each participant receives a Huawei Band 10 smart wristband that monitors heart rate, fall events, and blood pressure via Bluetooth synchronisation to the community health management platform. Training completion is recorded through WeChat-based manual check-in. A WeChat mini-programme delivers daily training prescriptions with illustrated guidance. The system includes automated training reminders and safety alerts (abnormal heart-rate detection triggers rest prompts and staff notification).

Personnel support: trained staff provide in-person guidance during the first week, with monthly on-site supervision thereafter. A designated team member contacts each participant weekly via WeChat to address questions and maintain adherence. Health education includes monthly group lectures and weekly one-on-one technique correction sessions.

Safety measures: pre-training medical screening (physical examination and exercise-risk assessment), individualised modifications for comorbidities (e.g., extended warm-up and blood-pressure monitoring for hypertensive patients), on-site emergency equipment (first-aid kit, AED), and a formal adverse-event reporting mechanism with monthly review and immediate reporting of serious events to the ethics committee.

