4.3.2 Control group

The control group receives standard health education without systematic RT. Activities include monthly 60-minute bone-health lectures (OP pathophysiology, nutritional guidance, fall-prevention strategies), delivered by hospital orthopaedic and community clinic staff, with

printed educational materials. Group discussion sessions are held every 4 months. Weekly telephone or WeChat follow-up by research staff provides general health advice (e.g., daily 20–30 minute walks), maintaining comparable contact frequency without introducing RT. This “attention control” design ensures that contact and engagement levels are balanced between groups.

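### Section 4.4.2 adds a fall-detection channel to the fall IRR that, on the most natural reading, only the intervention arm has, and section 3.3.2 defines the same outcome without it

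*Protocol*

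**What the plan says.** Falls are a secondary outcome, and the protocol describes their ascertainment twice.

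- **Section 4.4.2 (secondary outcomes):** "cumulative falls recorded via smart-terminal feedback and monthly follow-up; incidence rate ratio [IRR] with 95% CI". Two sources feed the count, and the arms are compared by a rate ratio.
- **Section 3.3.2 (dependent variables):** "fall incidence (monthly fall diaries and telephone follow-up". No device appears.

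Two further sections show who has what equipment.

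- **Section 4.3.1 (intervention group, smart components):** "each participant receives a Huawei Band 10 smart wristband that monitors heart rate, fall events, and blood pressure via Bluetooth synchronisation", linked to the community platform.
- **Section 4.3.2 (control group):** "The control group receives standard health education without systematic RT". It then itemises lectures, printed material, group discussions and personal contact: "Weekly telephone or WeChat follow-up by research staff provides general health advice". It lists no wristband, terminal or platform. The balance it claims is that the design "ensures that contact and engagement levels are balanced between groups", which does not extend to how falls are detected.

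**The concern.** A rate ratio compares like with like only if an identical fall has the same chance of being recorded in either arm. If one arm has an automatic channel on top of the shared follow-up, falls that participants forget or do not mention can still enter the count in that arm and not in the other. Randomisation balances the risk of falling but not the chance that a fall is recorded. Blinding the outcome assessors does not help either, because the extra records arrive before any assessor is involved.

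The device effect runs against the intervention. A real reduction in falls could be diluted or lost, or an apparent excess of falls could be read as a safety signal in a training programme for people with osteoporosis. Fall prevention is a prominent part of the rationale in sections 1.3.2 and 2.1.5, so readers will look at this result even though it is secondary.

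**Working it through.** The protocol states no fall rate, target IRR, device sensitivity or power for falls, so there is no figure to reproduce. The check has two parts.

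**1. The text, source by source**

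| Source of fall reports | Intervention arm | Control arm |
|---|---|---|
| Monthly follow-up (4.4.2); diaries and telephone (3.3.2) | yes, no restriction by arm | yes, no restriction by arm |
| Smart-terminal feedback (4.4.2) | yes, if this means the wristband of 4.3.1 | nothing listed in 4.3.2 |

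No section limits the between-arm comparison to falls found by the shared source. Section 4.4.3 standardises DXA, functional tests, questionnaires and grip strength, but not fall ascertainment.

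**2. Size of the effect, by illustration**

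Simple form: observed IRR = true IRR × relative capture (intervention ÷ control). Assume that the device adds 10–30% to recorded falls in the intervention arm:

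- true IRR 1.00: 1.00 × 1.10 = 1.10 and 1.00 × 1.30 = 1.30
- true IRR 0.80 (assumed): 0.80 × 1.10 = 0.88 and 0.80 × 1.30 = 1.04

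Structured form: let s be the share of true falls that follow-up catches, equal in both arms. Let d be the share of the missed falls that the device catches in the intervention arm. Both are assumptions. Then

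relative capture = [s + (1 − s)d] / s

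With d = 0.50:

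- s = 0.60: (0.60 + 0.40 × 0.50) / 0.60 = 0.80 / 0.60 = 1.33
- s = 0.75: (0.75 + 0.25 × 0.50) / 0.75 = 0.875 / 0.75 = 1.17
- s = 0.90: (0.90 + 0.10 × 0.50) / 0.90 = 0.95 / 0.90 = 1.06

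Over s = 0.60 to 0.90 and d = 0.25 to 0.75, relative capture runs from (0.90 + 0.10 × 0.25) / 0.90 = 1.03 to (0.60 + 0.40 × 0.75) / 0.60 = 1.50. With s = 0.75 and d = 0.75 it is (0.75 + 0.25 × 0.75) / 0.75 = 1.25, and a true IRR of 0.80 is then seen as 0.80 × 1.25 = 1.00.

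If falls are counted only from the shared source, d = 0 and relative capture is s / s = 1.00. The observed IRR then equals the true IRR, provided s really is the same in both arms. The more complete the monthly follow-up, the less the device can add.

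**The case against.** The strongest reply is that the protocol nowhere says that the smart terminal is the wristband, or that controls lack it. The term is undefined in section 4.4.2 and used loosely elsewhere. Section 1.2.3 treats smart terminals as user interfaces, apart from health-monitoring sensors. Section 2.4.4 spreads a smart terminal's cost over 10 user-sessions, which sounds like shared equipment. The study centres already have smart-care infrastructure (4.1.3) and recruitment draws on their databases (4.2.3), so a channel open to both arms is not excluded. Section 4.3.1 also speaks of each participant. This stands as a limit on certainty: the wristband reading is an inference. It remains the more natural one, because section 1.3.4 describes the data-acquisition layer as wearable terminals, the wristband is issued in the intervention section, and the itemised control content contains no device.

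Three stronger readings are tempting, and the documents do not support them.

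- *Falls are counted by the device alone.* Section 4.4.2 also names monthly follow-up, which is not limited to one arm. Only the device's additional captures differ.
- *False alarms inflate the count.* If unverified alerts counted, the distortion would be larger: with s = 0.75, d = 0.50 and 0.10 false alarms per true fall, (0.875 + 0.10) / 0.75 = 1.30. But the protocol does not say whether an alert counts unconfirmed, so this is a possibility only.
- *The trial's main conclusions are at risk.* The primary outcomes are lumbar spine BMD, SPPB and SF-36, none of H1–H6 concerns fall incidence, and the device effect would work against the intervention rather than create a false benefit.

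It could also be said that a statistical analysis plan will settle the matter. An analysis rule helps only if the source of each fall is recorded. Ascertainment is a data-collection rule, and this protocol already states it in two incompatible ways.

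**Conclusion.** The point holds at moderate severity. The conflict between sections 3.3.2 and 4.4.2 is plain on the text. Unequal detection follows if section 4.4.2 is applied as written and the smart terminal is the wristband, which is the most natural reading but is not stated outright. In that case the IRR is pushed upward by the device's contribution beyond follow-up. How far is unknown: the 10–30% extra capture and the values of s and d are all assumptions, and they show the direction and sensitivity of the IRR rather than an expected bias.

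**What to change.** Reconcile sections 3.3.2 and 4.4.2. For the IRR, count falls only from the monthly diary and telephone follow-up, collected on the same schedule with the same questions in both arms. Remove smart-terminal feedback from the IRR definition in 4.4.2, and report falls found only by the device separately as safety or process data. The safety alerts themselves need no change. If the sponsor intends both arms to have the device, section 4.3.2 must say so and 4.4.2 should define the term.

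The edit is about one sentence, and ethical approval is still pending (section 4.7.1), so it is easy to make now. The cost is that some true falls seen only by the device leave the efficacy count. A small difference may also remain, because a participant contacted after an alert is more likely to remember and report that fall.

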4.4.3 Measurement standardisation

DXA: all scans performed on the same device with daily phantom calibration; L1–L4 region-of-interest placement by certified technicians following a uniform protocol; same-technician longitudinal measurement preferred. Functional assessments: evaluators complete standardised training with inter-rater reliability verified ($ICC > 0.90$); test conditions (chair height, walkway length) are held constant. Questionnaires: validated Chinese-language versions administered under neutral guidance; immediate completeness checks. Equipment calibration: grip dynamometer calibrated before use; standardised seated position with 90° elbow flexion, best of two trials recorded. Quality assurance: all personnel certified prior to data collection; monthly data-quality meetings address and correct procedural issues.

4.5 Data Management and Quality Control

4.5.1 Data collection

Data are collected primarily through an electronic case report form (eCRF) system. Assessors enter measurements directly into tablet-based electronic forms with pre-defined range and logic checks. Each participant receives a unique identification code; names are excluded to protect privacy and maintain blinding. Paper CRFs serve as backup and undergo double data entry within 24 hours. Real-time backups to a central cloud server (Jianguoyun) are supplemented by weekly offline archives.

4.5.2 Data entry and storage

Dual-entry verification identifies discrepancies for correction against original records. The project database resides on an encrypted cloud server (Jianguoyun) with AES-256 encryption, role-based access control (PI: full access; field assessors: data-entry only), and audit-trail logging. Daily automated backups to an off-site server and weekly encrypted hard-drive archives ensure data security. All procedures comply with China's Personal Information Protection Law; analytical datasets are stripped of direct identifiers.

4.5.3 Data cleaning

Missing data: distributions and patterns are reported for all key variables. Little's MCAR test assesses missingness mechanisms; if data are missing at random (MAR), multiple imputation is used for sensitivity analysis. Linear mixed models in the primary analysis accommodate incomplete data. Outliers: identified through distribution plots and box plots, verified against original records, and handled according to pre-specified rules: confirmed errors are corrected, physiologically implausible values are excluded, and plausible extreme values are retained with

robust or sensitivity analyses (e.g., Winsorisation). All exclusions and modifications are documented.

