1.3.3 Current research landscape and limitations

Despite robust evidence for the efficacy of RT, critical gaps remain in study design and real-world implementation, particularly regarding long-term effects, community feasibility, adherence, and cost-effectiveness. Most RCTs employ intervention periods of 12 months or shorter, with a notable absence of follow-up studies exceeding two years for adults aged over 75 or those meeting frailty criteria.

Community-based implementation faces multiple challenges. Infrastructure deficits constitute a core barrier; according to the 2023 China Urban–Rural Health Service Survey, only 28% of community centres are equipped for RT, falling below 10% in rural areas. Professional supervision is similarly scarce. With respect to adherence, six-month retention rates in non-trial settings commonly fall below 50%, influenced by transportation barriers, scheduling difficulties, monotonous exercise modalities, and the absence of incentive structures.

In health economics, long-term data supporting the cost-effectiveness of community-delivered RT remain unavailable. Significant inter-individual variation—linked to baseline vitamin D levels, sarcopenia status, and VDR genotype polymorphisms—is poorly accounted for, and systematic models for individualised training parameters are lacking. Integration of smart technologies is still at an early stage; most wearable devices are limited to step counting and heart-rate monitoring without adaptive feedback. The digital divide further constrains the

uptake of technology-enhanced training among older adults.

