3.2.4 H4 (Sub-study 4)

Technology acceptance moderates intervention effects, mediated through training adherence. Participants with greater smart-device experience and more positive attitudes towards the training platform maintain higher adherence and achieve greater BMD and functional improvements; conversely, participants lacking technological experience or finding device use difficult may discontinue training, thereby attenuating overall intervention effectiveness.

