4.1 Study Design Overview

4.1.1 Primary study design

This study employs a two-arm, parallel-group, assessor-blinded randomised controlled trial (RCT), with 1:1 allocation to the intervention and control groups. Outcome assessors are blinded to group assignment to minimise measurement bias. The protocol and reporting adhere to the CONSORT 2010 Statement, including transparent documentation of randomisation sequence generation, allocation concealment, blinding, and participant flow.

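### The missing-data sensitivity analysis hangs on a test that cannot establish MAR, and it repeats the assumption of the primary mixed model

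*Protocol*

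**What the plan says.** Protocol section 4.5.3 (Data cleaning) fixes three things about missing outcomes.

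- The mechanism is judged with Little's MCAR test, and "if data are missing at random (MAR), multiple imputation is used for sensitivity analysis".
- The primary analysis relies on the model itself: "Linear mixed models in the primary analysis accommodate incomplete data".
- The amount and pattern of missing data are to be described for the key variables.

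The section's other sensitivity analyses, "robust or sensitivity analyses (e.g., Winsorisation" and the like, concern extreme values, not missing ones. It does not say what happens if the data are judged not to be MAR.

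Two other places bear on how plausible informative missingness is. Section 3.2.4 (H4) expects that "participants lacking technological experience or finding device use difficult may discontinue training, thereby attenuating overall intervention effectiveness". Section 1.3.3 notes, as background, that "six-month retention rates in non-trial settings commonly fall below 50" per cent. Neither states a dropout rate for assessments in this trial.

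**The concern.** The rule asks a test to settle something it cannot settle. MAR and MNAR differ only in how missingness relates to values nobody observed, so no test on the observed data separates them. A decision that begins by asking whether the data are MAR therefore cannot be taken from Little's test.

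The analysis behind the gate has a second weakness. A likelihood-based mixed model is already valid under MAR. Imputing under MAR and re-estimating asks nearly the same question again. If the people without an 8-month scan did worse than their observed data predict, both analyses miss it by about the same amount, and their agreement may be reported as robustness.

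What is at stake is the credibility of the 8-month comparison on the primary outcomes (lumbar spine BMD, SPPB, and SF-36 PCS and MCS). Section 3.3.4 adds to this by making the 4-month DXA conditional on resources. Some participants without an 8-month scan may have only a baseline BMD, and MAR then carries more of the weight.

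**Working it through.** **1. What each result of Little's test would license.** The null is MCAR.

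| Result | What it supports | What it leaves open |
|---|---|---|
| Rejects | Data are not MCAR | MAR or MNAR |
| Does not reject | No evidence against MCAR | MCAR, undetected MAR, or MNAR |

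Neither row delivers the condition in section 4.5.3. If rejection is read as MAR, MNAR data that also reject are misclassified. If non-rejection is read as harmless, MNAR data that do not reject get no sensitivity analysis.

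**2. Assumptions side by side.** Primary mixed model: MAR given the variables in the model (a property of the method; the protocol does not name it). Imputation as stated: MAR given the variables in the imputation model, with none named beyond the outcome model. With the same variables, the two assumptions coincide.

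**3. Illustrative simulation.** The protocol gives no sample size, SD or dropout figure, so there is nothing of its own to reproduce. Inputs from the protocol: two arms "with 1:1 allocation to the intervention and control groups", and the 3% BMD gain in section 1.4.1, taken here as the true between-arm difference. Assumed: 48 per arm (section 1.4.4 only hints at fewer than 100 in total); SD of BMD percentage change 3 at 4 months and 4 at 8 months, correlation 0.6; 20% or 30% missing at 8 months in the intervention arm; 10% MCAR in control; 20 imputations without auxiliaries; 1,500 runs per row. Little's test is applied in the intervention arm at the 5% level. MNAR dropout depends on the part of the 8-month value not predicted by the 4-month value.

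| Mechanism, intervention dropout | Little's test rejects | Full data | Mixed model | MI under MAR |
|---|---|---|---|---|
| MCAR, 20% | 5% | 3.03 | 3.04 | 3.04 |
| MCAR, 30% | 5% | 2.96 | 2.97 | 2.97 |
| MAR, 20% | 85% | 2.97 | 2.98 | 2.98 |
| MAR, 30% | 94% | 2.99 | 2.99 | 2.99 |
| MNAR, 20% | 5% | 2.97 | 3.71 | 3.71 |
| MNAR, 30% | 5% | 2.96 | 4.01 | 4.01 |

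The test rejected most often where both analyses were unbiased, and no more often than its nominal level where both were biased: 3.71 − 2.97 = 0.74 and 4.01 − 2.96 = 1.05 points. The 5% under MNAR follows from the chosen mechanism. Other MNAR mechanisms would lead to rejection, but would then look like MAR. The two estimates agree to two decimals in every row.

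**4. Simple size of bias.** Let d be the fraction missing in an arm and s the shortfall of the missing participants against their MAR prediction. Then

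bias in the difference ≈ d(intervention) × s(intervention) − d(control) × s(control).

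Setting the control term to zero, with assumed d and s:

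| d \ s | 1 point | 2 points | 3 points |
|---|---|---|---|
| 10% | 0.1 | 0.2 | 0.3 |
| 20% | 0.2 | 0.4 | 0.6 |
| 30% | 0.3 | 0.6 | 0.9 |

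Against the 3% expected gain this runs from 0.1/3 = 3% to 0.9/3 = 30%. The simulated biases lie above the grid because that mechanism is stronger: 0.74/0.20 = 3.7 and 1.05/0.30 = 3.5 points of implied shortfall.

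**The case against.** The best counter-argument is that this is a short data-cleaning paragraph. Departure-from-MAR analyses are commonly left to a statistical analysis plan, which may exist. That stands as far as it goes: a reader might infer that informative dropout will never be examined in this trial, and the protocol alone does not support that. No analysis tests for MNAR in any case; one can only explore assumptions about it. The point is therefore limited to the rule the protocol does state. A later plan would either inherit an invalid condition or contradict it.

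Other parts also stand:

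- **Limited reach.** The gate decides only whether a secondary imputation is run. The mixed model is primary regardless, and missing-data patterns are described either way.
- **Auxiliary variables.** Imputation could draw on adherence logs, eHLQ and TAM scores, or 4-month function, all of which section 3.3.4 collects. It could then differ from the mixed model and make MAR more plausible. The protocol neither plans nor excludes this, and the simulated agreement depends on leaving them out.
- **Section 3.2.4 is about stopping training.** A reader might infer that the protocol itself predicts informative loss of 8-month scans and an overstated effect. It does not. People who stop training can still be measured, and the section expects a weaker effect. Overstatement needs the added assumption that they also miss the assessment and do worse than predicted.
- **The figures are assumed.** Similar informative dropout in the control arm would offset the bias.

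**Conclusion.** The concern holds for the stated rule. Little's test cannot supply the MAR condition. Imputation under MAR without added auxiliary variables does not stress the assumption of the primary mixed model, so agreement between them is not evidence against bias from informative dropout. Nothing else in this protocol departs from MAR for missing data. These conclusions follow from the methods and do not depend on any assumed number.

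The size is unknown. The range of 0.1–0.9 points of BMD percentage change rests wholly on an assumed 10–30% intervention-arm dropout, a 1–3 point shortfall and no informative dropout in control. The larger simulated values rest on a stronger assumed mechanism. None of these forecasts the trial's bias, and the documents do not show that the primary estimate will be wrong. The rule is worth correcting, but it does not invalidate the primary analysis.

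**What to change.** In section 4.5.3:

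1. Remove Little's test as a condition. It may stay as a descriptive summary.
2. State that the primary linear mixed model assumes MAR given the variables it includes.
3. Commit to at least one sensitivity analysis that departs from MAR, run whatever the test shows. A suitable choice is delta-adjusted multiple imputation for lumbar spine BMD at T2 (8 months). It lowers the imputed intervention-arm values step by step until the conclusion changes, and reports that tipping point. Extend it to SPPB, PCS and MCS.
4. If imputation under MAR is kept, name the auxiliary variables that let it add something to the mixed model.

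Reference-based imputation is an optional alternative, not a requirement. The delta range and other details can go in the statistical analysis plan.

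The cost is a few sentences and some extra programming and reporting, with no new data. Section 4.7.1 lists ethical approval as pending, so the wording can be changed cheaply now.
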